Formative and Pilot Intervention Research for Prevention and Treatment of HIV/AIDS (R34 Clinical Trial Option):

HIV Risk Reduction Intervention for Transwomen with Intimate Partner Victimization

Investigators:

[name] (local PI), [name] (former PI / Co-I), [name], [name]

Sponsor:

National Institute of Health

1. Background

- Transgender women (TW) are among the populations most heavily affected by HIV in the United States (US), with nearly 1 in 5 TW living with HIV.
- IPV is a pervasive public health problem for transgender people. Results of the 2015 US Transgender Survey (USTS) indicated that over half (54%) of TW experience lifetime IPV, and comparative research shows elevated IPV rates among transgender people compared with their cisgender counterparts.
- IPV is associated with increased HIV risk due to greater likelihood of condomless sex, sex with high-risk partners (e.g., who are HIV-positive or who inject drugs), and compromised condom negotiation skills, as well as high rates of posttraumatic stress disorder (PTSD) and substance use disorder (SUD) which are also associated with HIV risk behaviors. Despite the dual and interconnected risks of HIV and IPV among TW, there are few empirically based HIV prevention interventions that target TW, and none that target HIV risks related to IPV in this population.
- To address syndemics of HIV and IPV, multicomponent interventions that target relevant risk factors and that consider population-specific vulnerabilities are needed.

2. Study Objective

The purpose of this treatment development research is to develop a brief intervention that concurrently targets HIV and IPV risk, as well as addresses inter-related risks of HIV and IPV (e.g., substance use and PTSD) for TW – referred to as Supporting Transwomen Affirmation, Relationships and Sex (STARS). STARS will:

- Be based on the Gender Affirmation Framework, which emphasizes interpersonal processes to positively affirm the identities and unique needs of TW.
- Integrate a trauma-informed empowerment approach.
- Include gender-affirming and empowering HIV prevention counseling that addresses HIV risk within the context of IPV and related risk factors (e.g., substance use and PTSD), and a range of HIV risk reduction options.
- Provide TW with behavioral skills and resources for addressing IPV and maximizing personal safety.

3. Study Aims

The aims of this treatment development research are to:

- (1) Develop a behavioral intervention manual that addresses the specific and unique HIV prevention needs of TW with IPV, and that uses a gender-affirmative, empowering, and trauma-informed approach**
- (2) Evaluate the feasibility, acceptability, safety, and initial effects of STARS through three phases of intervention development.**

We are primarily interested in exploring the pattern of results for any evidence of support for the intervention's influence on our primary and secondary outcomes.

Long-term aim: The findings from this R34 intervention development study will provide the groundwork to examine the efficacy of STARS in a future, large-scale clinical trial, which can be readily implemented in real-world settings.

4. Description of Study Design, Materials and Methods

4.1 Study Design

Phase 1, Initial Development: Employ qualitative methods to strengthen our understanding of the dynamics between HIV risk and IPV among TW, and use those findings to develop a STARS manual, interventionist training protocol, and fidelity scales.

Phase 2, Open Trial: Conduct an open pilot of the STARS protocol and use cognitive interviewing techniques to refine the STARS manual, interventionist training protocol, and fidelity scales, based on participant feedback.

Phase 3, Pilot RCT: Conduct a pilot test of the STARS protocol using a two-arm trial comparing effects of the STARS intervention vs Relaxation Training (a validated time and attention matched control) over 6-months of follow up with respect to our primary and secondary outcomes.

4.2 Study Procedures

Phase 1 (Year 1 & 2, April 2021 – June 2022)

General Overview

- Formative phase
- Development of STARS
- Focus group and informant interviews
- Feedback on STARS
- Fidelity
- Interventions training and fidelity

Participants/eligibility

- Individuals will be eligible if they are:
 - (1) 18+ years old;
 - (2) Assigned male at birth but identify as female, transgender, or transfeminine;
 - (3) Endorse at least one IPV incident during the previous 12 months based on the Conflict Tactic Scales-Revised (CTS-2; Straus, 2017) or the trans-specific IPV Scale (T-IPV Scale; Peitzmeier et al, in press);
 - (4) Report at least one instance of condomless anal sex in the last 3 months.
- Individuals will be considered ineligible if they:
 - (1) Have been diagnosed with HIV or test positive for HIV.
- Individuals expressing interest in the research will undergo brief screening by telephone and then complete a more detailed in-person eligibility assessment prior to enrollment.
- All participants will provide informed consent prior to initiating the study protocol.

Recruitment & Retention

- All research activities will take place in Providence, Rhode Island metropolitan area
- Participant reimbursement:
 - Focus group participants will receive \$30 reimbursement and a brochure with a list of TW-sensitive HIV testing sites and other social/health services upon completing the study.
 - Key informants will receive \$30 upon completing the study.

- Multifaceted recruitment approach: online advertisements in social media for TW audiences, placing fliers in targeted venues, and conducting in-person outreach to agencies, clinics, bars and community events.
- Retention strategies: close communication and collaboration with CBOs that serve local TW and hiring an outreach specialist from within the local trans community.

Procedures

- Develop/design a preliminary manual for STARS and control (relaxation training; RT).
- Conduct focus groups and individual interviews (if applicable) with TW with HIV risk and IPV ($n = 18$) to understand ways of increasing acceptability and efficacy of STARS and acceptability of RT for this population.
- Designate specific benchmarks to determine if additional focus groups are needed to further develop STARS.
- Solicit feedback on STARS from participants, and community experts/key informants that provide services for TW.
- Solicit feedback from participants regarding barriers to attending sessions and brainstorm methods to address barriers and maximize attendance.
- Assess the acceptability and feasibility of booster sessions, including their number, length, timing, and setting (i.e., phone-calls vs. in person).
- Make changes to STARS based on feedback
- Develop STARS and RT interventionist training protocol and fidelity scales.

Analysis

- Focus groups and interviews (if applicable) will be audio-recorded, transcribed and coded using qualitative analysis.
- A descriptive summary will be developed to represent key content of the focus group.

Phase 2 (Year 2, June – February 2023)

General Overview

- Refinement phase: gain experience with the screening, assessment and intervention to inform subsequent refinement of protocol and procedures
- Cognitive interviewing and open pilot (nonrandomized)

Participants/eligibility

- Individuals will be eligible if they are:
 - (1) 18+ years old;
 - (2) Assigned male at birth but identify as female, transgender, or transfeminine;
 - (3) Endorse at least one IPV incident during the previous 12 months based on the Conflict Tactic Scales-Revised (CTS-2; Straus, 2017) or the trans-specific IPV Scale (T-IPV Scale; Peitzmeier et al, in press);
 - (4) Report at least one instance of condomless anal sex in the last 3 months.
- Individuals will be considered ineligible if they:
 - (1) Have been diagnosed with HIV or test positive for HIV.
- Individuals expressing interest in the research will undergo brief screening online or by telephone and then complete a more detailed in-person eligibility assessment prior to enrollment.
- All participants will provide informed consent prior to initiating the study protocol.

Recruitment & Retention

- All research activities will take place online via Zoom and/or in Providence, Rhode Island metropolitan area

- Participant reimbursement: Participants will receive \$75 for their first assessment and \$50 for their second and third assessments as reimbursement (\$175 total), as well as a brochure with a list of TW-sensitive HIV testing sites and other social/health services. All transportation required for the study will also be covered using study funds.
- Multifaceted recruitment approach: online advertisements in social media for TW audiences, placing fliers in targeted venues, and conducting in-person outreach to agencies, clinics, bars and community events.
- Retention strategies: close communication and collaboration with CBOs that serve local TW and hiring an outreach specialist from within the local trans community.

Procedures

- Pilot STARS among TW ($n=5-8$) with elevated HIV risk and IPV.
- Elicit feedback via exit interviews (structured informant interview and evaluation surveys) to finalize STARS protocol and research procedures.
- Refine and finalize STARS manual, interventionist training protocol, and fidelity scales using participant feedback and acceptability and feasibility metrics.

Analysis

- Detailed notes of IDI exit interviews will be analyzed (consider recording) to review feedback and make final adjustments
- At the end of phase 2, compute descriptive data on all target outcomes in Table 1 and discuss how actual outcomes compare to target outcomes.
- Discrepancies will result in: 1) investigation of the reason for failure to meet this outcome, and 2) discussion among the research team.

[figure not shown]
Table 1. Target Outcomes	
Description (Assessment method)	Target
Feasibility and Acceptability— SAS, RT	
Acceptability (End of Intervention Survey; see C10.3)	Endorsing an average score of 3 or more (out of 5) for each rated intervention component)
Satisfaction (Client Satisfaction Questionnaire-8; see C10.3)	Average > 24 (or a mean score of 3 on each of the 8 items)
Intervention attendance	70% of all participants complete at the initial session and at least 2 of 3 booster sessions
Intervention Fidelity (see C8.4)	SAS and RT interventions achieve at least 80% adherence on a random subset of sessions
Safety	
Adverse events	No serious adverse events or injuries that are possibly, probably, or definitely related to study participation.
Feasibility and Acceptability—Research Procedures	
Recruitment rate	Average of 3-4 enrolled per month
STI testing procedures	80% of participants complete STI testing procedures at baseline and 70% at 6-month follow-up
Timeliness of assessments	80% of follow-up assessments occur within 3-weeks of due date
Completeness of self-report instruments and interviews	Self-report instruments have 80% of items completed and interviews 90% of items completed in 90% of cases
Retention rate	80% complete 3-mo and 70% complete 6-mo f/u assessments
Participant burden	Qualitative responses from exit interviews do not suggest undue burden of intervention or research procedures

Phase 3 (Years 1-4, October 2021 – July 2024)

General Overview

- Pilot RCT phase: two-arm, randomized, controlled design with up to 50 TW.
- Participants will be followed for up to 6-months post enrollment with assessments taking place at T1: Baseline; T2: Post-intervention; T3: 4-months follow up; and T4: 6-months follow up.
- Refer to Figure 1 below for the study flow
- The control group will be given an attention and time-matched control condition focused on relaxation and stress reduction.
- Both the STARS intervention and the control protocol consist of two one-hour sessions held one week apart and two brief 20-30 minute booster sessions held two- and four-weeks after the 2nd hour long session.
- Both interventions are designed to be delivered by peer counselors. Requirements for peer counselors include identifying as trans women or trans feminine and having leadership roles in the trans community.

Figure 1. STARS - Phase 3: Randomized Controlled Trial (RCT) Study Flow Chart

Participants/eligibility

- Individuals will be eligible if they are:
 - (1) 18+ years old;
 - (2) Assigned male at birth but identify as female, transgender, or transfeminine;

- (3) Endorse at least one IPV incident during the previous 12 months based on the Conflict Tactic Scales-Revised (CTS-2; Straus, 2017) or the trans-specific IPV Scale (T-IPV Scale; Peitzmeier et al, in press);
- (4) Report at least one instance of condomless anal sex in the last 6-months.
- Individuals will be considered ineligible if they:
 - (1) Have been diagnosed with HIV or test positive for HIV.
- Individuals expressing interest in the research will undergo brief screening online or by telephone and then complete a more detailed in-person eligibility assessment prior to enrollment.
- All participants will provide informed consent prior to initiating the study protocol.

Recruitment

- All research activities will take place online via Zoom and/or in Providence, Rhode Island metropolitan area
- Multifaceted recruitment approach: online advertisements in social media for TW audiences, placing fliers in targeted venues, and conducting in-person outreach to agencies, clinics, bars and community events.
- Retention strategies: close communication and collaboration with CBOs that serve local TW and hiring an outreach specialist from within the local trans community.

Compensation

- Participant reimbursement: Participants will have an opportunity to earn up to \$250 in total – they will receive \$50 for completing the T1: baseline assessment; \$50 for the T2: post-intervention assessment, \$25 for the exit interview; \$50 for the T3: 4-month follow up; \$50 for the T4: 6-month assessment; and a \$25 bonus if they complete all four assessments (T1-T4).
- Participants will be given the option to receive their compensation in the form of an Amazon gift card or on a VISA clincard.

Procedures

- Conduct a randomized pilot trial of STARS in 50 TW with elevated HIV risk and IPV to demonstrate the (a) feasibility, (b) acceptability, and (c) safety of the intervention.
- Examine preliminary evidence that relative to an attention and time matched control, STARS will result in improvements in our:
 - Primary outcomes;
 - Secondary outcomes; and
 - Mechanisms of change consistent with the theoretical foundations of the intervention, including greater perceived gender affirmation, and increases in empowerment and self-efficacy.
- Test, diagnose and (if positive) treat baseline STIs (and HIV) prior to initiating the STARS program. The research staff will work with participants to find gender-affirming health care clinics in their area that provide free or low-cost STI and HIV testing. Participants will be encouraged to

get tested for STIs as part of the research study; however, STI testing is not a requirement for participation.

- Complete a baseline behavioral and psychosocial baseline survey assessments administered via ACASI. Refer to the Phase 3 RCT Measures document for the complete list of standardized measures administered at baseline and at follow up.
- Upon completion of the baseline assessment, participants will be randomized to either the Intervention (STARS) condition or to a time-attention matched control (see details below).
 - **STARS Intervention** (*the final version of STARS was developed through an iterative process and refined/finalized by findings from Phases 1 and 2*)
 - Participants randomized to STARS will participate in a brief intervention immediately following the baseline (BL) assessment consisting of two one-hour sessions held one week apart and two brief 20-30 minute booster sessions held two- and four-weeks after the 2nd hour long session.
 - Participants will develop personalized risk reduction plan (RRP), which will include participants identifying “next steps” for reducing their HIV and IPV related risks.
 - Booster sessions will include a review of the RRP, identification and reinforcement of accomplishments, as well as identification of and problem solving around any social barriers to the RRP.
 - The RRP will be revised based on identified accomplishments and social barriers at each booster session.
 - **Control Intervention**
 - Participants randomized to the time-attention matched control condition will participate in a relaxation and stress reduction intervention that also consists of two one-hour sessions held one week apart and two brief 20-30 minute booster sessions held two- and four-weeks after the 2nd hour long session.
 - Content will serve to keep the RA blind to participant condition and will include a series of guided relaxations (e.g., breathing meditation, visual imagery).
 - During booster sessions, the interventionist will review participants’ success with their relaxation plan and identify further strategies to integrate relaxation into daily lives.

Analysis

- At 2-time points during phase 3, compute descriptive data on all target outcomes in Table 1 and discuss how actual outcomes compare to target outcomes.
Discrepancies will result in: 1) investigation of the reason for failure to meet this outcome, and 2) discussion among the research team.

4.3 Measures (Phases 2 & 3) -- For the complete list of standardized measures administered at baseline and at follow up time points, refer to the Phase 3 RCT Measures document.

Acceptability:

- 8-item Client Satisfaction Questionnaire-Revised (CSQ-8-R) (Attkisson & Zwick, 1982) will be used to assess satisfaction with the intervention.
- An End of Intervention Questionnaire (EIQ) will be developed that will assess the perceived helpfulness of intervention components.
- These scales will be administered to both conditions after the initial 90-min intervention (PI), as well as after each booster session.
- Exit interviews will be conducted with participants randomized to the STARS intervention.

Primary Outcomes:

(1) **Composite Risk for HIV (CR-HIV)** is a binary indicator of any HIV risk (e.g., yes=1 vs. no=0), which is an algorithm based on whether the participant:

- report condomless anal sex with a HIV serodiscordant or status-unknown primary or other partner in the past 3 months;
- is using PrEP;
- is in a monogamous partnership with an HIV-uninfected partner or an ;
- is in a monogamous partnership with an HIV-infected partner who is virally suppressed.
- If participants are not certain about the latter two indicators, they are coded as having HIV risk according to this algorithm.

(2) **IPV frequency** will be assessed with:

- The Composite Abuse Scale revised short form (CASr-SF).and
- A trans-specific IPV Scale (T-IPV Scale; Peitzmeier et al, in press) that assesses IPV unique to TW (e.g., being forced not pursuing aspects of gender transition that you wanted).

(3) **IPV safety** will be assessed with the:

- Measure Of Victim Empowerment Related to Safety (MOVERS; Goodman et al., 2015), which is a 13-item scale that measures IPV survivors' safety-related psychosocial skills and efficacy and expectations of support, as well as the extent to which survivors feel that their efforts to achieve safety might create new difficulties.

Secondary Outcomes:

- **Biologically determined STI diagnoses, including HIV** - The research staff will work with participants to find gender-affirming health care clinics in their area that provide free or low-cost STI and HIV testing. Participants will be encouraged to get tested for STIs as part of the research

study; however, STI testing is not a requirement for participation. HIV self-test kits will be mailed to willing participants and the research staff will walk participants through testing procedures as well as post-test result counseling (as needed) over Zoom or in-person.

- Self-reported discrete **behavioral risk indicators**: CAS, multiple and concurrent partnerships, partners' HIV status, monogamy and sexual agreements, substance use including injection drug use, HIV testing behaviors (including self-testing) and knowledge, intentions to use PrEP, PrEP uptake, use of any HIV prevention services, and use of any additional IPV-related services/resources.

Exploratory Tertiary Outcome/Potential Mediators: Refer to the Phase 3 RCT Measures document for the complete list of standardized measures administered at baseline and at follow up time points.

5. Dissemination

- Throughout the study, we will disseminate process reports and descriptive summaries of the findings to colleagues at social service and medical/health agencies with whom we established MOUs.
- As data are evaluated, we will prepare brief reports describing the major findings from the study which we will share with our community partners, HIV prevention and IPV scientists, and TW health and advocacy organizations through publications and presentations at professional conferences.

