HIV Risk Reduction Intervention for Transwomen with Intimate Partner Victimization:

Statistical Analysis Plan

Descriptive statistics will be used to characterize the study sample and compare baseline differences between intervention conditions. Fidelity to intervention protocols will be assessed using adherence and competence ratings on approximately 5% of all completed sessions, balanced across peer counselors and study. Feasibility will be quantified based on retention and attrition rates, which will be visualized in a CONSORT diagram.

To explore the preliminary efficacy of the intervention, mean values for key study outcomes (i.e., empowerment, IPV frequency, PTSD symptoms, depressive symptoms, and HIV vulnerability) will be plotted across study time points (baseline, post- intervention, 4-month, and 6-month follow-ups). We additionally will test for intervention effects using intent-to-treat models with all available data. Linear mixed models (LMMs) with maximum likelihood estimation will be used for continuous outcomes (e.g., empowerment, PTSD symptoms, and depressive symptoms). Count-based outcomes (e.g., past-2-month frequency of IPV, past-60-day number of HIV-vulnerable sex acts) will be dichotomized to indicate any vs. no occurrence (0 = none, 1 = any instance). These binary outcomes will be modeled using GLMMs with a binomial distribution and logit link function. All models will include fixed effects for condition, time, and condition \times time interactions. Any significant baseline demographic differences will be included as covariates in the final models. An unstructured covariance matrix will be used to account for within-participant correlations across time points.

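### The only safety criterion counts SAEs and injuries judged related, without reference to arm, and the SAP has no adverse-event analysis, so the target can be met while SAEs or injuries are more frequent under STARS

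*Protocol*

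**What the plan says.** Protocol 4.2, Phase 3 Procedures, says that the randomised pilot is meant to "demonstrate the (a) feasibility, (b) acceptability, and (c) safety of the intervention". The only safety target is in Table 1, which is set out under Phase 2 (the nonrandomised open pilot): "No serious adverse events or injuries that are possibly, probably, or definitely related to study participation". It names no arm.

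The Phase 3 Analysis paragraph carries the table into the RCT: "At 2-time points during phase 3, compute descriptive data on all target outcomes in Table 1". If a target is missed, "Discrepancies will result in: 1) investigation of the reason for failure to meet this outcome, and 2) discussion among the research team".

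The RCT is a "two-arm, randomized, controlled design with up to 50 TW". The allocation ratio is not stated. To be eligible, a participant must "Endorse at least one IPV incident during the previous 12 months".

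The SAP plots "key study outcomes (i.e., empowerment, IPV frequency, PTSD symptoms, depressive symptoms, and HIV vulnerability") over the four visits. It then fits intent-to-treat mixed models with condition, time and their interaction. Counts, including IPV over the past two months, are first reduced to any versus none. The SAP does not mention adverse events, injuries or safety. Neither document says who judges relatedness, whether that person is blind to arm, or how an assault by a partner is to be classified.

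**The concern.** The criterion rests on a causal judgement made one event at a time. In this population that judgement is unusually hard. Recent partner violence is an entry requirement, so some injuries are likely in both arms whatever the treatment. STARS also asks participants to plan steps that bear on their IPV risk, and such steps could provoke a partner. The protocol recognises this possibility: its description of MOVERS (section 4.3) includes whether acting to become safer brings fresh problems. When a participant is injured after such a step, nothing in the single case shows whether the injury would have happened anyway.

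Randomisation offers a comparison that needs no attribution: all SAEs and injuries in one arm against all in the other. The plan does not specify it. Team discussion is triggered only by a missed target, so if every event is judged unrelated, nothing in the plan prompts a look at the two arms. The safety conclusion matters beyond this study, because the protocol intends the results as groundwork for a large efficacy trial.

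**Working it through.** The documents give no event rate, power or confidence limit for safety, so there is no planned figure to reproduce. The inputs are up to 50 participants in two arms (Protocol 4.2, Phase 3) and the zero-event target (Table 1). Equal allocation, hence 25 per arm, is an assumption. So are all event rates below.

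**1. How far the target depends on attribution.** Let q be the risk that a STARS participant has an SAE or injury provoked by STARS, and a the chance that it is judged at least possibly related. Assume also that no other event is judged related. Then P(target met) = (1 − q·a)^25.

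| a | q = 8% | q = 12% |
|---|---|---|
| 1 | 0.92^25 = 12% | 0.88^25 = 4% |
| 0.5 | 0.96^25 = 36% | 0.94^25 = 21% |
| 0.25 | 0.98^25 = 60% | 0.97^25 = 47% |
| 0.1 | 0.992^25 = 82% | 0.988^25 = 74% |
| 0 | 100% | 100% |

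For the same true harm, the chance of meeting the target runs from 4% to 100% at q = 12%. The judgement that moves it has no stated rule.

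**2. What zero events would show.** The exact two-sided 95% upper limit with 0 of n is 1 − 0.025^(1/n). For n = 25 this is 1 − 0.025^(1/25) = 13.7%. (The one-sided 95% limit, 1 − 0.05^(1/25), is 11.3%.) If the true risk were 5%, zero events in 25 would still occur with probability 0.95^25 = 28%.

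**3. What a by-arm table would add.** Suppose 8 of 25 STARS and 3 of 25 control participants have an SAE or injury, and none is judged related. The Table 1 target is met. The table would show 32% against 12%, a difference of 0.20. Its standard error is √(0.32·0.68/25 + 0.12·0.88/25) = 0.114, which gives a 95% CI of 0.20 ± 1.96·0.114, or −0.02 to 0.42 (Fisher p = 0.17). The imbalance becomes visible, with its uncertainty.

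**4. What it would not add.** At two-sided 0.05 with 25 per arm, exact Fisher power is 8.6% for 10% versus 20% and 30.5% for 10% versus 30%. By the normal approximation, 80% power for 10% versus 30% needs 62 per arm. The table estimates harm; it cannot exclude it.

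**5. Whether the efficacy models fill the gap.** A participant coded 1 for IPV at baseline can only stay at 1 or fall to 0, so more frequent or more severe violence leaves her value unchanged. The model can register new IPV in participants coded 0 at baseline, but not escalation in those coded 1.

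**The case against.** The strongest reply is that harm is already compared by arm. IPV frequency and MOVERS are primary outcomes (Protocol 4.3), and the SAP models IPV, PTSD and depressive symptoms by condition regardless of cause. A reader might infer from the Table 1 row that the plan makes no randomised comparison of partner violence at all. The documents do not support that. What remains is narrower: SAEs and injuries are not compared by arm, the modelled outcomes are not tied to the safety row, and the coding of IPV hides escalation.

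Second, the row includes events only possibly related, which is a low threshold. A reader might infer that the plan directs staff to put an assault down to the partner. No text does so. The missing rule leaves that outcome open, no more.

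Third, Table 1 is descriptive. The protocol neither requires nor rules out showing it by arm, and nothing declares STARS safe once the target is met. That is fair, but a comparison that bears on a stated aim should be specified in advance.

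Fourth, one might combine the 70% six-month retention target with the zero-event limit and quote a limit for 17 or 18 people. That would treat anyone who misses the last visit as unobserved throughout. The sessions and boosters end about five weeks after the first session (one week plus four), so participants lost later still contribute the treatment period.

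Fifth, the control arm has only about 25 people and cannot settle the question of harm. This stands, and it limits the fix to estimation.

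**Conclusion.** The concern holds in a limited form and should be addressed. For a stated Phase 3 aim, the only criterion depends on attribution and names no arm, and the SAP has no adverse-event analysis. In a population selected for recent IPV, the target can be met while SAEs or injuries are more frequent under STARS. Under the assumed 12% risk of provoked events, the chance of meeting it is 4% if every event is judged related and 47% if a quarter are.

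Even with perfect attribution, zero events in an assumed 25 STARS participants is compatible with a risk of up to 13.7%. The trial can estimate the rate of harms with limits; it cannot demonstrate safety. The 25 per arm rests on 1:1 allocation and full enrolment, and the event and attribution rates are illustrations, not forecasts.

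**What to change.** Keep the Table 1 target as it is. Add to the SAP:

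- A table by randomised arm giving the number and percentage of participants with any SAE or injury regardless of attributed cause, and with any judged at least possibly related. Give exact 95% CIs, the difference between arms, and the number observed.
- CASr-SF and T-IPV scores by arm, not only any versus none, reported as a safety outcome.

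Base the Phase 3 safety statement on this table, and in Protocol 4.2 describe the aim as estimating harms with their limits instead of demonstrating safety.

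The cost is one SAP paragraph and one table. The IPV scales are already planned. An event has to be recorded before its relatedness can be judged, so the event data should exist, but neither document states that all injuries are logged and this should be confirmed. The comparison will be descriptive and underpowered at about 25 per arm, and the safety claim becomes slightly less favourable.

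### The Table 1 burden target rests on exit interviews assigned to the STARS arm alone, so it has no control-arm data, and the stated $250 maximum payment is out of reach for controls

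*Protocol*

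**What the plan says.** Four parts of the protocol bear on this point.

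- **Who is interviewed.** Under Acceptability in Section 4.3, the satisfaction and end-of-intervention questionnaires go to both arms: "These scales will be administered to both conditions after the initial 90-min intervention (PI), as well as after each booster session". The next bullet reads: "Exit interviews will be conducted with participants randomized to the STARS intervention". The control arm is not mentioned there.
- **What the interviews are used for.** In Table 1 the participant-burden target is: "Qualitative responses from exit interviews do not suggest undue burden of intervention or research procedures". No other data source is named. The row sits in the block on research procedures. The Phase 3 analysis text in Section 4.2 requires descriptive data on all Table 1 targets at two time points.
- **What is paid.** The Phase 3 compensation text says: "Participants will have an opportunity to earn up to \$250 in total". It itemises $50 for each of T1 to T4, $25 "for the exit interview", and a $25 bonus for completing all four assessments. It makes no distinction by arm.
- **Matching and blinding.** The Phase 3 overview says: "The control group will be given an attention and time-matched control condition focused on relaxation and stress reduction". The control description adds: "Content will serve to keep the RA blind to participant condition".

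The SAP mentions neither burden nor exit interviews. It quantifies feasibility by retention and attrition.

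**The concern.** Feasibility and acceptability are stated purposes of this pilot, and burden is one of the pre-specified targets by which they will be judged. Table 1 was first applied in the open pilot of Phase 2, where every participant received STARS, so exit interviews covered everyone. Phase 3 carries the same target into a two-arm trial but assigns the interviews to one arm.

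The target will therefore be declared met or missed on STARS participants alone. If controls found the assessments tiresome, or the relaxation sessions a poor use of time, this benchmark would not show it. A future trial needs to know that, because an unacceptable comparator tends to lose participants from one arm.

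The payment text raises a separate, smaller matter. A maximum offered to participants in general should be attainable in either arm, or be stated by arm.

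**Working it through.** **Step 1. Reproduce the stated maximum.** Inputs are from the Phase 3 compensation text: T1 $50, T2 $50, exit interview $25, T3 $50, T4 $50, completion bonus $25.

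50 + 50 + 25 + 50 + 50 + 25 = $250, which matches the protocol's figure.

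**Step 2. Remove the exit interview, as Section 4.3 implies for controls.**

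250 − 25 = $225. The gap of $25 is 25/250 = 10% of the STARS maximum, or 25/225 = 11% of the control maximum. The bonus depends on T1 to T4 only and is the same in both arms.

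**Step 3. Trace the burden target to its data.**

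- Table 1: burden is judged from exit interviews and covers intervention and research procedures.
- Phase 3 analysis: all Table 1 targets are to be computed.
- Section 4.3: exit interviews are for those randomized to STARS. The word *only* is not used, but the bullet just before names both conditions, so a STARS-only reading is the natural one.

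Together these give no control-arm burden data. The protocol says up to 50 participants and gives no allocation ratio. Assuming 1:1 and full enrolment, 50/2 = 25 participants contribute nothing to the target.

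**Step 4. Check session time.** Both arms have two one-hour sessions and two boosters of 20 to 30 minutes.

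2 × 60 + 2 × 20 = 160 minutes, and 2 × 60 + 2 × 30 = 180 minutes. The range is the same in each arm.

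**Step 5. Size the one-arm contact.** The interview's length is not stated. Assuming 15 to 60 minutes, it would equal between 15/180 = 8% and 60/160 = 38% of session time. This range reflects the assumption more than the plan, and it leaves out the assessment contact at T1 to T4 that both arms share.

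**Step 6. Check timing.** The payment list puts the interview after T2 and before T3. If that order is chronological, the payments available before T3 are 50 + 50 + 25 = $125 in STARS and 50 + 50 = $100 in control. No date is given, and the Phase 3 flow chart is not reproduced in the text available here.

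**The case against.** The case against has four parts.

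*The target can be computed as written.* It is defined by exit-interview responses, and those will exist. STARS participants follow the same T1 to T4 schedule as controls, so their answers do inform research burden. Controls also contribute satisfaction and helpfulness ratings, and they count towards retention, timeliness and completeness. All of this is fair and narrows the gap. It does not close it: none of those measures asks about burden, and STARS participants cannot report on the burden of the relaxation intervention.

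*A reader might infer that the interview breaks the attention matching or acts as an extra booster.* The documents do not support this. Matching is claimed for the intervention conditions, and their session time is equal. The interview is listed among the acceptability measures. Its content is not described, whereas boosters are separately defined by their own content.

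*A reader might infer that the research assistant is unblinded, or that the $25 raises STARS retention.* No text says who schedules, runs or pays for the interviews. The $25 is not conditional on attending T3 or T4, and the place before T3 rests on list order alone. These remain possibilities to guard against, not defects shown. Even on that timing, the T2 comparison, which the SAP also models, is untouched.

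*Moving the interviews after T4 would be no clean cure.* The 6-month retention target is 70%, so up to 30% could go uninterviewed while that target was still met, plausibly including those who found the study most burdensome. An earlier Phase 3 review of Table 1 would also lack burden data. This stands, and the fix below does not rely on moving them.

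**Conclusion.** The point holds in a limited form. A pre-specified feasibility target that covers procedures common to both arms has no stated data source in the control arm, and the $250 maximum is correct only for STARS, where controls can reach $225. Both conclusions rest on reading Section 4.3 as STARS-only, which the contrast with the preceding bullet supports. The figure of 25 participants without burden data further assumes 1:1 allocation of 50.

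The protocol refers to a separate Phase 3 measures document that is not among those reviewed. If it already contains burden items for both arms, Table 1 should name them as a source.

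The documents do not show broken attention matching, actual unblinding or an effect on retention, and this point claims none of these. It is a cheap improvement to the trial's answer on feasibility, not a threat to the comparison between arms.

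**What to change.** 1. **Give the burden target control-arm data.** Preferably, add a few short burden questions to the T2 and T4 surveys in both arms, and define the Table 1 target on these together with the STARS interviews. Asking at T2 as well as T4 captures some participants who later drop out. Alternatively, offer the same exit interview and $25 to both arms, with the research-burden questions in common.
2. **Reconcile the Phase 3 compensation text with Section 4.3.** State who is interviewed and paid, and give the correct maximum for each arm.
3. **As a secondary precaution, state when the interviews take place and who handles them.** Existing staff other than the blinded research assistant should schedule, run and pay for them. If they do fall before T3 in one arm only, report this as a one-arm research contact when interpreting retention and outcomes at T3 and T4.

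Cost: the survey route makes two surveys slightly longer. Interviewing both arms costs up to 25 × $25 = $625 in payments (assuming 1:1 allocation of 50), plus time for interviewing and coding. The payment correction is a change of wording.
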